Physical examination	X										X
Injections at study site											
PK injection (80 IU/kg BW) [10]		X									
IVR injection			X	X	X		X		X		X
Start of prophylactic treatment phase [8]		X									
Local laboratory assessments											
Routine safety laboratory (haematology)	X										X [3]
Determination of AB0 blood group			X [4]								
Central laboratory assessments											
VWF:Ac (VWF:RCo)	X	X [6]	X [2]	X [2]	X [2]		X [2]		X [2]		X [2]
FVIII:C (OS)		X [6]	X [2]	X [2]	X [2]		X [2]		X [2]		X [2]
VWF and FVIII inhibitors [5]	X				X [3]		X [3]		X [3]		X [3]
Retention samples for virus marker testing	X										
VWF multimer analysis	X	X [7]									
Haemophilia Joint Health Score (HJHS) [9]	X										X
Assessment of compliance and adherence to treatment regimen		X	X	X	X	X	X	X	X	X	X

ASSESSMENTS	Screening Visit	PK Visit (within 4 weeks after Screening)	1-Month Visit (±3 days)	2-Month Visit (±3 days)	3-Month Visit (±1 week)	Compliance Call 1 [1] (5–7 weeks after 3-Month Visit)	6-Month Visit (±2 weeks)	Compliance Call 2 [1] (5–7 weeks after 6-Month Visit)	9-Month Visit (±2 weeks)	Compliance Call 3 [1] (5–7 weeks after 9-Month Visit)	Study Completion (12-Month) Visit (+2 weeks)
Bleeding Episodes monitoring	Throughout the study										
Concomitant Medication monitoring	Throughout the study										
Adverse event monitoring	Throughout the study										

VWD = von Willebrand disease, FVIII = factor VIII, FVIII:C = factor VIII procoagulant activity, OS = one-stage assay

[1] Parents should be contacted by telephone 5–7 weeks after the 3-monthly IVR visits at 3, 6, and 9 months to check the patient's status of bleedings, AEs, concomitant medications, compliance and adherence with treatment regimen, including the evaluation of the need to adjust the prophylactic treatment, completing diary.

[2] Within 60 min before and 15 ±5 min after *wilate* injection.

[3] Before injection.

[4] To be determined unless known.

[5] At the given time-points and at any time if inhibitor development is suspected.

[6] Blood samples for PK and recovery assessment to be taken before injection, and after 15 minutes, 3, 9, 24, 48 and 72 hours after injection (central laboratory). At least three different *wilate* batches should be used.

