3.1.3 Safety Parameters

Secondary Endpoints

- Incidence of VWF and FVIII inhibitors
- Incidence of thromboembolic events
- Joint Health Status determination by the use of the HJHS, given the patient's age and constitutional development allow this assessment
- Safety and tolerability of *wilate* assessed by monitoring AEs throughout the study

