6.1.9 Unscheduled Visits and Additional Measures

If inhibitor development is suspected (e.g. based on an unexplained need to increase the dose, a lack of efficacy of *wilate* injections seen in more frequent spontaneous bleeds, or prolonged bleeding), VWF and FVIII inhibitor tests will be performed at the central laboratory and will be documented accordingly (see **Section 7.4.5.1**).

In case of positive inhibitor result, inhibitor re-testing using a second, separately drawn sample should be performed, preferably within 15 days of becoming aware of the positive result, and further measures will need to be discussed on an individual basis. If the result is confirmed, the patient will be discontinued from the study.

Other reasons for unscheduled visits may be the occurrence of serious AEs or hospitalisations for BEs or surgical interventions.

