7.4.5.1 Central Laboratory

The following laboratory parameters will be determined in accordance with the time points specified in **Table 1** and in **Section 6**, and as shown in the Laboratory Sampling Flowchart in **Table 10**:

- **FVIII:C (one-stage)** in *wilate* batches used for PK/IVR evaluations will be determined (for VWF:Ac (VWF:RCo), potency will be obtained from the Certificates of Analysis).
- **FVIII:C** will be measured in plasma at pre-specified time points using the OS assay.
- **VWF:Ac** will be measured in plasma at pre-specified time points by VWF:RCo.
- For **VWF** and **FVIII inhibitor titre testing**, a sample will be analysed at the central laboratory. In addition, VWF and FVIII inhibitor testing will be performed testing at baseline, every 3 months, and in case of inhibitor suspicion.
- A retention sample is to be drawn for possible virus marker testing.
- Multimer distribution of the VWF by multimer analysis using low- and high resolution electrophoresis gels (preferably 1% and >2% gels) in paediatric patients with VWD type 3 and a body weight ≥ 14.5 kg; VWF multimers will be determined by a quantitative method.

Central laboratory facilities:

Main blood sample reception laboratory for EMEA countries:

Labcorp Central Laboratory Services S.à.r.l.

[name]
[name]

Main blood sample reception laboratory for US / CA:

Labcorp Central Laboratory Services

Limited Partnership

[name]

[name]

Analysis of central laboratory parameters:

VWF:Ac (RCo), FVIII (OS), VWF Inhibitors, FVIII Inhibitors;

LabCorp Esoterix Coagulation Laboratory

[name]

[name]

[name]

Analysis of central laboratory parameter:

VWF Multimer Analysis

MEDILYS Laborgesellschaft mbH

[name]

[name]

Laboratory kits for all required central laboratory tests are provided by Labcorp Central Laboratory Services in Indianapolis, US.

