4.8.3 Laboratory variables

The analysis of the safety parameters (lab values for Haematology) recorded during visits and at surgery will be purely descriptive and presented as summary tables or listings.

Time profiles of the safety laboratory parameters will be analysed by presenting sampling statistics for the values as well as their difference to baseline at each time point. Additionally, frequency tables for values outside the normal ranges will be presented.

Time profiles of the safety laboratory parameters will be analysed by presenting sampling statistics for the values as well as frequency tables for positive findings.

Similarly, time profiles of VWF and FVIII inhibitor testing results will be analysed by presenting sampling statistics for the values as well as frequency tables for number of positive findings, along with 95% Pearson-Clopper CIs.

The thromboembolic risk will be monitored by determination of VWF:Ac during the study and especially postoperatively. Descriptive statistics including changes to pre-infusion will be presented by visit and timepoint (with 95% CI) for visits or by operative day and timepoint for surgeries, respectively.

A by subject list of all abnormal lab values will be displayed. In analyses only scheduled, common time points will be displayed. Results from unscheduled visits will only be used in listings. In such listings the normal ranges as well as an indicator of H/L and CLS will be given.

Statistical Analysis Plan	Version 2.0		Page 19 of 27
Sponsor	Octapharma	Protocol No	WIL-33

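### SAP 4.8.3 keeps on-suspicion inhibitor tests and their re-tests out of the inhibitor table and its confidence interval, so a confirmed inhibitor may go uncounted in a named secondary endpoint

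*SAP*

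**What the plan says.** Protocol 3.1.3 lists "Incidence of VWF and FVIII inhibitors" among the secondary safety endpoints.

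The protocol finds inhibitors by two routes. Table 1 schedules samples at Screening and at the 3-, 6-, 9- and 12-month visits, and its footnote 5 widens this: "At the given time-points and at any time if inhibitor development is suspected". Protocol 7.4.5.1 agrees: "VWF and FVIII inhibitor testing will be performed testing at baseline, every 3 months, and in case of inhibitor suspicion". The second route is described in Protocol 6.1.9, the section on unscheduled visits: when an inhibitor is suspected, "VWF and FVIII inhibitor tests will be performed at the central laboratory and will be documented accordingly". After a positive result, "inhibitor re-testing using a second, separately drawn sample should be performed, preferably within 15 days of becoming aware of the positive result". The consequence follows: "If the result is confirmed, the patient will be discontinued from the study".

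On the analysis side, SAP 4.8.3 says that "time profiles of VWF and FVIII inhibitor testing results will be analysed by presenting sampling statistics for the values as well as frequency tables" of positive findings, with 95% Clopper-Pearson intervals. Protocol 9.2.3 plans the same output. Later in SAP 4.8.3 comes a rule that Protocol 9.2.3 does not contain: "In analyses only scheduled, common time points will be displayed. Results from unscheduled visits will only be used in listings". The section makes no exception for inhibitor tests.

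**The concern.** The rule suits routine by-visit laboratory summaries, where irregular samples would distort a time profile. Applied to inhibitors, it removes the samples that were drawn because of a safety signal: Protocol 6.1.9 gives unexplained dose need, loss of efficacy and prolonged bleeding as reasons to suspect an inhibitor. Leaving those samples out can only lower the number of children counted as positive.

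Two features make the loss hard to recover. Confirmation leads to discontinuation, so later scheduled samples may never be taken. And the SAP defines no per-child count across visits, so a series of by-visit rows is the only inhibitor-specific output. With about a dozen children, one case separates a report of no inhibitors observed from a report of a signal.

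**Working it through.** **No figure to reproduce.** Neither document states an expected inhibitor rate, and both say that no formal sample size calculation was done. The check is a trace of one hypothetical case through the stated rules, followed by exact intervals.

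**Inputs**
- Planned number of children: 12, of whom at least 8 evaluable (SAP 1.4). The actual size of the safety set is not given, so N = 12 and N = 8 are used as assumptions.
- Scheduled post-baseline inhibitor tests: months 3, 6, 9 and 12 (Protocol Table 1).
- Intervals: two-sided 95% (SAP 4), Clopper-Pearson (SAP 4.8.3).
- Number of cases: one, seen only on unscheduled samples. This is an assumption.

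**Trace, N = 12.** Suppose a child is negative at month 3, is tested on suspicion between months 3 and 6, is positive, and is confirmed on a second sample.

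| Sample | Where SAP 4.8.3 puts it |
|---|---|
| Month 3, negative | By-visit row: 0/12 |
| On-suspicion test, positive | Listing only |
| Re-test, positive | Listing only |
| Months 6, 9, 12 | Not taken if the child has left: 0/11 per row |
| Study Completion Visit at withdrawal, if attended | Not stated |

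The last line matters. Protocol 6.1.7 invites early withdrawals to that visit, which includes central inhibitor testing. The SAP does not say whether an early completion visit counts as a scheduled, common time point.

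**Intervals.** For x positives among n, the lower limit is the 0.025 quantile of Beta(x, n − x + 1) and the upper limit is the 0.975 quantile of Beta(x + 1, n − x). Two special cases can be checked by hand:
- x = 0: the lower limit is 0 and the upper limit is 1 − 0.025^(1/n). For n = 12 this is 1 − 0.025^(1/12) = 26.5%; for n = 11 it is 28.5%.
- x = 1: the lower limit is 1 − 0.975^(1/n). For n = 12 this is 0.2%. The upper limit solves (1 − p)^12 + 12p(1 − p)^11 = 0.025, giving p = 38.5%.

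| Assumed N | Table without the case | Child counted once |
|---|---|---|
| 12 | 0/12 = 0% (0–26.5%) | 1/12 = 8.3% (0.2–38.5%) |
| 12, rows after the child leaves | 0/11 = 0% (0–28.5%) | – |
| 8 | 0/8 = 0% (0–36.9%) | 1/8 = 12.5% (0.3–52.7%) |

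One omitted case moves the estimate by 8.3 points at N = 12 and 12.5 points at N = 8. The upper limit moves by 38.5 − 26.5 = 12.0 and 52.7 − 36.9 = 15.8 points.

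**Comparison within the SAP.** SAP 4.8.1 builds its adverse event incidence tables from subjects with at least one occurrence while at risk, and gives thromboembolic events such a table. Inhibitors, listed beside thromboembolic events in Protocol 3.1.3, have no equivalent of their own.

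**The case against.** The strongest reply is that the case is not lost. Protocol 7.4.3 requires inhibitor development to be reported as an SAE. SAP 4.8.1 tabulates serious TEAEs per subject without restriction to scheduled visits, and lists SAEs and events leading to discontinuation. A reader of the report would therefore meet the case. This stands, and it limits the consequence. But the serious TEAE table carries no inhibitor confidence interval, and it would sit beside an inhibitor table that might read zero.

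Second, the child may still reach the inhibitor table: at the Study Completion Visit, at a later scheduled test, or because suspicion happened to coincide with a scheduled visit. This also stands. However, attendance at the early completion visit is by invitation, and the status of a sample taken there is undefined.

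Third, the rule sits among sentences about abnormal values and normal ranges, so it may have been written with routine laboratory parameters in mind. That is plausible, but the wording is general and it is in the same section as the only inhibitor-specific analysis.

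Finally, output specifications are kept in a separate list of tables, and parts of SAP 4 and 4.7.1 were not in the text available for this review. An any-time inhibitor row could exist in the separate list; the SAP as read does not require one.

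**Conclusion.** The point holds as a gap in the definition of a secondary safety endpoint. Following SAP 4.8.3 as written, positive on-suspicion tests and re-tests do not contribute to the inhibitor frequency table or its interval, and a confirmed case may be absent from both. Under the assumption of one such case, the table understates incidence by 8.3 points with 12 children and 12.5 points with 8. It should be corrected, but it does not touch the primary endpoint and the case remains visible as a serious TEAE.

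A reader might infer more than the documents support:
- That an inhibitor found on suspicion can never enter the table. The unscheduled result is barred; the child can still be counted through a scheduled or completion-visit sample.
- That most inhibitors would be found on suspicion before the next scheduled sample. The documents give no time from onset to suspicion, so the 3-monthly spacing alone cannot show which test comes first.
- That a type 3 inhibitor table would be affected. SAP 3.8 stratifies safety by sex only, so no such table is planned.
- That haematology needs the same remedy. Protocol Table 6 and SAP 4.8.3 also provide for laboratory values at surgery, so that situation differs and is not part of this point.

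**What to change.** In SAP 4.8.3, restrict the scheduled-time-points rule to by-visit summaries and state that VWF and FVIII inhibitor tests are exempt from the listings-only provision.

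Add one endpoint row per inhibitor type, VWF and FVIII:
- Numerator: children with a positive test at any time after first IMP, from scheduled or unscheduled samples, each child counted once. Show any positive, and positives confirmed on re-test.
- Denominator: children in the safety set tested at least once after first IMP.
- Interval: Clopper-Pearson 95%.

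Keep the by-visit table as support, and say whether a Study Completion Visit held at early withdrawal is treated as a scheduled time point.

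The cost is a small change to one SAP section and one row per inhibitor type. It needs no new samples and changes no clinical rule. The one drawback for the sponsor is that the reported incidence may be less favourable.

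### The scheduled-visits-only rule in SAP 4.8.3 can leave an inhibitor first found at an unscheduled test out of the only inhibitor table with a confidence interval

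*SAP*

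**What the plan says.** Protocol 3.1.3 lists "Incidence of VWF and FVIII inhibitors" among the secondary safety endpoints. Protocol 7.4.5.1 sets the timing: "VWF and FVIII inhibitor testing will be performed testing at baseline, every 3 months, and in case of inhibitor suspicion". The flow chart (Protocol Table 1, footnote 5) agrees: "At the given time-points and at any time if inhibitor development is suspected".

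Protocol 6.1.9, the section on unscheduled visits, covers both the suspicion-triggered test and what follows a positive: "inhibitor re-testing using a second, separately drawn sample should be performed, preferably within 15 days of becoming aware of the positive result". It continues: "If the result is confirmed, the patient will be discontinued from the study". Under Protocol 6.1.7, patients who leave early are invited to a completion visit, which includes an inhibitor test.

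SAP 4.8.3 handles haematology and inhibitors in one section. For inhibitors it plans time profiles with "frequency tables for number of positive findings, along with 95% Pearson-Clopper CIs". It then sets the display rule: "In analyses only scheduled, common time points will be displayed". The next sentence sends all other results to listings: "Results from unscheduled visits will only be used in listings". Protocol 9.2.3, which describes the same inhibitor analysis, has no such restriction.

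SAP 4.7.2 also names an inhibitor test 3 to 8 weeks after surgery, which may or may not fall on a scheduled visit.

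**The concern.** An incidence asks how many patients ever had the event. The table in SAP 4.8.3 answers a narrower question: how many were positive at each common visit. The two agree only if every inhibitor shows at a scheduled test.

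The protocol makes that uncertain. After the 3-month visit the scheduled tests are three months apart. The triggers for an extra test are an unexplained need for more product, more frequent spontaneous bleeding or prolonged bleeding. A case that shows itself clinically between visits would thus first be found at an unscheduled test. Once confirmed, the patient is discontinued and has no further regular visits at which the inhibitor could be counted.

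The retest is also normally an unscheduled sample. Without it, the table gives a confirmed inhibitor and an unrepeated positive the same weight. With about 12 patients, one case decides whether the table shows an inhibitor or none.

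**Working it through.** The documents state no inhibitor rate and no precision target, so there is no figure of the plan's own to reproduce. The check first follows each kind of test through the SAP rule, then shows what one misplaced case does to the interval.

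**Step 1. Where each result goes if SAP 4.8.3 is followed as written**

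| Source of result | Defined in | In the inhibitor frequency table? |
|---|---|---|
| Scheduled test at 3, 6, 9 or 12 months | Protocol Tables 1 and 10 | Yes |
| Suspicion-triggered test | Protocol 6.1.9; Table 1, footnote 5 | No, listing only |
| Post-surgery test at 3 to 8 weeks | SAP 4.7.2 | Only if it coincides with a scheduled visit. Otherwise it belongs to the surgery outputs, which are listings only unless more than 3 surgeries occur |
| Retest on a second sample | Protocol 6.1.9 | No, unless drawn at a scheduled visit |
| Completion visit at withdrawal | Protocol 6.1.7 | Possibly, if the family attends and the visit is mapped to a scheduled time point. Neither is assured |

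So a case is fully omitted when the first positive is at an unscheduled test and the withdrawal visit does not recapture it. If the first positive is at a scheduled visit, the case stays in the table and only the retest result is lost.

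**Step 2. Inputs**

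- Planned patients: 12, of whom 8 evaluable and at least 4 with type 3 disease (SAP 1.4).
- Interval: two-sided 95% Clopper-Pearson (SAP 4 and 4.8.3).
- Denominator: SAP 8.4 normally uses the patients assessed. After one discontinuation that is at most 12 − 1 = 11.
- Assumption: exactly one patient develops an inhibitor, and it is found only at an unscheduled test.

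**Step 3. Formulas**

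- For 0/n, the lower limit is 0 and the upper limit is 1 − 0.025^(1/n).
- For 1/n, the lower limit is 1 − 0.975^(1/n). The upper limit is the p that solves (1 − p)^n + n·p·(1 − p)^(n−1) = 0.025.

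**Step 4. Results**

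| n | All tests counted | Scheduled visits only |
|---|---|---|
| 12 | 1/12 = 8.3% (0.2 to 38.5) | 0/12 = 0% (0 to 26.5) |
| 12, assessed patients only | 1/12 = 8.3% (0.2 to 38.5) | 0/11 = 0% (0 to 28.5) |
| 8 | 1/8 = 12.5% (0.3 to 52.7) | 0/8 = 0% (0 to 36.9) |
| 4 (type 3 minimum) | 1/4 = 25.0% (0.6 to 80.6) | 0/4 = 0% (0 to 60.2) |

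For example, 1 − 0.025^(1/12) = 0.265 and 1 − 0.025^(1/11) = 0.285. With 12 patients the upper limit falls by 38.5 − 26.5 = 12.0 points, or by 38.5 − 28.5 = 10.0 points if only assessed patients count.

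**Step 5. The opposite error**

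Suppose one scheduled positive is not confirmed on the retest. The table shows 1/12 = 8.3% (0.2 to 38.5), while the confirmed incidence is 0/12 = 0% (0 to 26.5). This is the same pair of figures, reversed.

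**The case against.** The strongest reply is that the case is counted elsewhere. Protocol 7.4.3 makes the development of a VWF or FVIII inhibitor a reportable serious adverse event, and the waivers in Protocol 7.4.4 do not cover it. SAP 4.8.1 tabulates serious treatment-emergent events per patient with no scheduled-visit limit, lists serious events and those leading to discontinuation, and foresees narratives. This stands: the case should be visible in the report. However, SAP 4.8.1 plans no interval there. It gives thromboembolic events an incidence table of their own and inhibitors none. The serious-event table could show a case while the inhibitor table shows zero.

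A second reply is that a by-visit profile is ordinary display practice and that the listings-only sentence sits among wording suited to haematology. That is a possible reading, but the section covers both kinds of result and states no exception. No other inhibitor incidence is defined in SAP 4.8.3 or in the derivations of SAP 6.1.

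A third reply is that the withdrawal visit may recapture a persistent inhibitor. It may, but attendance is by invitation only.

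Finally, the full list of outputs is a separate document (SAP Appendix 1), and parts of SAP section 4 are not in the text available here. An any-time inhibitor summary could be specified in either.

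A reader might go further and infer that the rule biases the result in favour of the product. The documents do not support that. Omitted cases lower the tabulated rate and retained unconfirmed positives raise it, so no net direction is shown. Nor is every case with an unscheduled retest omitted, because a scheduled first positive is already counted.

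**Conclusion.** The point holds in a limited form. As written, SAP 4.8.3 can show no inhibitor in its only inhibitor table with an interval although one occurred, and it cannot separate confirmed from unconfirmed positives. The protocol's incidence endpoint therefore has no output that reliably estimates it.

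In a study of 12, one such case is the difference between 8.3% (0.2 to 38.5) and 0% (0 to 26.5, or about 28.5 with 11 assessed). These figures illustrate the size; they do not predict it. They assume one case, found only at an unscheduled test and not recaptured at a withdrawal visit.

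The serious-event route should keep the case in the report, so the likely damage is two tables that contradict each other and an interval that does not match the endpoint. This should be fixed, but it is not a fault that invalidates the safety analysis.

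**What to change.** In SAP 4.8.3, with the definitions added to the derivations in SAP 6.1:

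- Add a per-patient inhibitor incidence, separately for VWF and FVIII, in two forms: (a) any post-baseline positive, and (b) a positive confirmed on the second, separately drawn sample.
- Use every inhibitor test for it: scheduled, suspicion-triggered, post-surgery, confirmatory and withdrawal.
- Take as denominator the patients in the safety set with at least one post-baseline inhibitor test, with a two-sided 95% Clopper-Pearson interval.
- State that the listings-only rule for unscheduled results does not apply to inhibitors.
- Keep the by-visit profiles at scheduled time points as supporting output.

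The cost is a short change to the SAP and one summary table. No new visit, sample or data item is needed.
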